## **5- MATERIAL AND METHOD**

### **5.1- Study design**

It is a prospective clinical study to compare two implants from two different brands of a similar design for their implantation [tissue level] and to evaluate the marginal bone loss of each dental implant in mm. 96 patients will be analyzed (an expected N of 48 per group, hoping to reach at least 100 implants per arm). See calculation of N in point 5.7.

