### **5.2- Study population**

The patients will be collected from patients who attend the master's degree in medicine, surgery and Oral Implantology, requesting implant-supported treatment. The study population will consist of patients who require treatment with dental implants, either partially or completely edentulous and who accept their placement and participation in the study. 4.2.1 Inclusion / exclusion criteria

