**5.5.- Procedures**

**5.5.1 First session and recruitment**

In this first session, before starting surgery and prosthodontic treatment, a thorough medical history will be taken. Each patient will be examined by extra-oral and intra-oral examination, in addition to the evaluation of their respective orthopantomography and cone beam computed tomography (CBCT), to evaluate the level of height and width of the bone for the placement of dental implants. This process will be carried out by the main researcher and supervised by another expert in Dentistry. Study participants who meet the inclusion criteria will then be recruited and asked if they wish to participate. Each of them will be given the following records.

If the patient meets the criteria and is interested, they will sign the informed consent and will be randomized using a randomization table of 10 in 10 implants [e.g.: randomization table ABBAABBBAB] to place one type or another of implant:

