### 5.8.- Statistical analysis

The variable data will be entered into the Excel program of the Microsoft Office 2019 Package (Microsoft Corporation, Washington, USA, 2013) and will be analyzed with the SPSS 26.0 program for Windows (SPSS, Illinois, USA, 2019).

The data collected will be processed using the STATA 14.0 statistical package. A descriptive analysis of the qualitative and quantitative variables will be carried out. The Kolmogorov-Smirnov test will be used to analyze the normality of the measurements.

The relationship between bone loss and implant position will be analyzed using parametric t-test.

The level of statistical significance chosen is 5% ( $\alpha = 0.05$ ). To evaluate the association between the dependent variable bone loss from T0 to T2 and successive Ts and the independent variables implant A, Implant B placement, a multiple linear regression analysis will be used.

All variables considered to potentially affect the study relationship, such as sex, age, and smoking, will be used as control variables in the regression; the number of cigarettes per day, maxilla or mandible, ISQ [implant stability value] and contact of the mesial and distal implant (penseic ade dinets and/or implants by mesial and distal)

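### The regression in 5.8 has no patient term although about two implants per patient are hoped for: smoking's standard error is too small, and the brand test's error rate depends on an allocation unit that 5.5.1 leaves open

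*Protocol*

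**What the plan says.** - **Size (5.1).** "96 patients will be analyzed (an expected N of 48 per group, hoping to reach at least 100 implants per arm". The aim is "to evaluate the marginal bone loss of each dental implant in mm".
- **Population (5.2).** Patients may be "either partially or completely edentulous and who accept their placement and participation in the study", so several implants in one mouth are to be expected.
- **Allocation (5.5.1).** The subject of the sentence is the patient, who "will be randomized using a randomization table of 10 in 10 implants".
- **Sample size (5.7).** The 48 per group are called both subjects and implants, for a difference of 0.2 mm, SD 0.34, two-sided alpha 0.05, beta 0.2 and 5% loss.
- **Analysis (5.8).** Brand enters through "the independent variables implant A, Implant B placement, a multiple linear regression analysis will be used". On covariates: "All variables considered to potentially affect the study relationship, such as sex, age, and smoking, will be used as control variables in the regression", followed by "the number of cigarettes per day, maxilla or mandible, ISQ [implant stability value] and contact of the mesial and distal implant". Separately, "The relationship between bone loss and implant position will be analyzed using parametric t-test".
- **Objectives (4.2).** Smoking, systemic disease and periodontal disease are secondary objectives.
- **Justification (2).** This section speaks of 100 implants, without saying whether that is the total.

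The protocol nowhere mentions a patient effect, a clustered standard error or a rule of one implant per patient.

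**The concern.** The protocol does not state the unit of analysis, but its covariates imply it. Jaw, ISQ and mesial or distal contact belong to a single implant and have no one value for a patient with several, so the regression row must be an implant. Sex, age, smoking and cigarettes per day are then constant across the rows from one patient. Ordinary regression treats those rows as independent. If implants in the same mouth are positively correlated, the standard error of any patient-level term is too small.

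The effect on brand depends on how brand is allocated. If a whole patient receives one brand, brand is also a patient-level term and its test rejects too often. If implants are allocated singly, the error rate is about nominal. If the brands are balanced within a mouth, the test is conservative. Because 5.5.1 does not settle which applies, the type I error of the trial's main test is not fixed. The t-test for position depends in the same way on whether position varies within a mouth.

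**Working it through.** **1. The plan's own figure.** n = 2(1.96 + 0.8416)² × 0.34² / 0.2² = 45.4 per group; 45.4 / 0.95 = 47.8, so 48. The stated figure reproduces, but the formula holds only for independent units.

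**2. Cluster size.** At the size hoped for in 5.1: 200 implants / 96 patients = 2.08 per patient.

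**3. Assumptions not in the protocol.** Within-patient correlation (ICC) 0.1, 0.3 or 0.5; 24 of 96 patients smoke; implants per patient either nearly equal (2 or 3 each) or uneven (1 plus a Poisson count, overall mean 2.08).

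**4. Closed form for a patient-level term.** The design effect is DE = 1 + (E[m²]/E[m] − 1) × ICC, where m is the number of implants per patient. The actual level of a nominal 5% test is 2(1 − Φ(1.96/√DE)). For uneven counts E[m²] = 1.083 + 2.083² = 5.42, so E[m²]/E[m] = 2.60. The equal-count row uses m = 2.08 throughout. The last row takes section 2's 100 implants as the total, with 92 patients having one and 4 having two: E[m²]/E[m] = 108/100 = 1.08.

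| Counts | DE at ICC 0.1, 0.3, 0.5 | Actual level |
|---|---|---|
| Equal | 1.11, 1.33, 1.54 | 6.3%, 8.9%, 11.4% |
| Uneven | 1.16, 1.48, 1.80 | 6.9%, 10.7%, 14.4% |
| 100 implants in all | 1.01, 1.02, 1.04 | 5.1%, 5.3%, 5.5% |

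**5. Simulation of the named regression under no effect.** 96 patients, SD 0.34, bone loss on brand, smoking and jaw, 12,000 runs per setting, uneven counts. Rejection rates at ICC 0.1, 0.3, 0.5:

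| Allocation of brand | Brand | Smoking |
|---|---|---|
| Whole patients, 48/48 | 6.7%, 10.4%, 14.3% | 6.8%, 10.7%, 14.7% |
| Single implants, blocks of 10 | 5.2%, 4.8%, 4.0% | 6.7%, 11.1%, 13.9% |
| Alternating within a mouth | 4.4%, 2.7%, 1.6% | 6.8%, 10.6%, 13.4% |

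With equal counts, smoking is at about 6%, 9% and 11%, and brand under whole-patient allocation at 6.6%, 8.8% and 11.9%. With a harsher skew (1 to 8 implants per patient, still 200 in all), smoking reaches about 8%, 13% and 18–19%. With 100 implants in all, brand is at 4.8% to 5.5% and smoking at 5.3% to 5.8%.

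**6. Standard errors.** For smoking, with whole-patient allocation and uneven counts, the model's mean standard error is 0.93, 0.82 and 0.74 of the true one.

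**7. Power.** With whole-patient allocation, 100 implants per arm and 5% loss (n = 95/DE per arm), power for 0.2 mm falls from 97% to 90% (equal counts) or from 96% to 85% (uneven) as the ICC rises from 0.1 to 0.5. Power is not the problem.

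**8. Does a patient term repair it?** A random patient intercept fitted by REML, with uneven counts and all three allocations (3,000 runs per setting), rejects 4.3% to 5.4% for brand and 4.2% to 5.7% for smoking. Patient-clustered standard errors give 4.2% to 5.7% and 5.6% to 6.9%. With the harsher skew, a simpler random-intercept fit leaves smoking at 5.6% to 7.1% and brand allocated by patient at 6.3% to 6.9%: much better than without it, though not exact.

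**The case against.** The strongest reply is that 5.8 names only a class of model. Clustered standard errors are compatible with multiple linear regression, and an analysis plan not shown here could add them. This does not remove the point. The protocol chose the model and its covariates, mixing patient-level and implant-level ones, and carrying it out as written gives wrong standard errors.

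Second, the clustering rests on one of three counts. Section 5.1 only hopes for 100 implants per arm, 5.7 treats subject and implant as the same, and section 2 gives 100 implants. With one implant per patient the problem vanishes, and with 100 implants in all it nearly does. That is correct, and it is why the counts must be reconciled. But 5.1 is the section that describes the design, and it aims for about two per patient.

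Third, the brand test is inflated only under whole-patient allocation, and a table that counts implants suggests otherwise. That stands. For brand the finding is that the error rate is undetermined, not that it is known to be inflated.

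Fourth, the ICC, the number of smokers and the spread of implant counts are all assumed. That also stands: the direction for smoking is certain for any ICC above zero, but the size is a range. The effect on the position t-test was reasoned, not calculated.

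Finally, 5.8 refers to several time points. If these enter one model, a patient intercept alone would not cover the correlation among repeated measurements of the same implant.

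**Conclusion.** The concern holds. At the size hoped for in 5.1, with the implant as the regression row and any positive within-patient correlation, the regression in 5.8 calls smoking significant too often whichever way brand is allocated: about 6–7% at ICC 0.1, 9–11% at 0.3 and 11–15% at 0.5, against a nominal 5%. Sex, age and cigarettes per day are affected in the same way. Systemic and periodontal disease would be too if analysed per implant, although 5.8 names no analysis for them.

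For the main brand comparison, the error rate ranges from under 2% to over 14% across the allocation schemes and ICCs examined, and the protocol does not say which scheme applies. More patients would not cure this, because the standard error itself is wrong. The conclusion rests on the inferred unit of analysis, on more than one implant in many patients, and on an ICC above zero; the figures rest on the assumed ICC, smoker number and implant counts.

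**What to change.** - **5.5.1:** state whether brand is allocated per patient or per implant.
- **5.7:** state whether 48 per group means patients or implants, and reconcile the counts in sections 2, 5.1 and 5.7.
- **5.8:** state that the implant is the unit of analysis, and use a linear mixed model with a random patient intercept for brand, position and the patient-level factors. Keep jaw, ISQ and mesial/distal contact as implant-level covariates. Regression with patient-clustered standard errors is acceptable, though slightly less exact for smoking. If several time points enter one model, add a term for the implant within the patient.
- If only one implant per patient is to be analysed, say so; the present regression then needs no patient term.

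The cost is wording in five sections and a different standard procedure in SPSS or Stata, with no extra patients. At ICC 0.1, 0.3 and 0.5 with uneven counts, the confidence interval for smoking widens by 7%, 18% and 27%. The interval for brand widens by 7%, 18% and 28% if whole patients are allocated, but narrows by 2%, 7% and 17% if single implants are allocated in blocks of 10.

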## **4-OBJECTIVES**

### **4.1 Main objective:**

To evaluate marginal bone loss in two different brands of implants placed at the bone level.

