### **4.2 Secondary objectives:**

- Relationship between marginal bone loss and suprabony soft tissue in mm.
- Relationship between marginal bone loss and ISQ value at the time of implantation.
- Relationship between marginal bone loss and torque (in Newton) at the time of implantation.
- Relationship between marginal bone loss and implant location.
- Relationship between marginal bone loss and the degree of periodontal disease.
- Relationship between marginal bone loss and systemic diseases.
- Relationship between marginal bone loss and smoking

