### 5.5.3 Third session

The patient will come to the Hospital to operate the surgery within 15-20 days after having the study cast revised by a dentist and specialist from the fixed department. The patient will have a temporary prosthesis (Fixed or Removable) after the surgery of the implant. A periapical X-Ray will be taken immediately after the surgery to control the marginal bone loss. With respect to accepted criteria for the assessment of implant success were proposed by Albrektsson and colleagues (Albrektsson *et al.*, 1986), which to identify clinical evidence of successful osseointegration and survival of implants, suggested that a marginal bone loss of less than 1.5 mm in the first year and 0.2 mm in the following years is acceptable after implant loading.

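### The implant A/B regression adjusts for ISQ, which is measured on the allocated implant after randomisation, so its coefficient need not be the brand effect the main objective asks for

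*Protocol*

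**What the plan says.** The main objective (Protocol 4.1) is "To evaluate marginal bone loss in two different brands of implants placed at the bone level".

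The order of events is as follows:

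- **First session (5.5.1).** Eligible patients "they will sign the informed consent and will be randomized" to one implant type or the other.
- **Third session (5.5.3).** "The patient will come to the Hospital to operate the surgery within 15-20 days" of the study cast being reviewed.
- **ISQ.** Section 4.2 sets as a secondary objective the "Relationship between marginal bone loss and ISQ value at the time of implantation", so the reading is taken at that surgery.

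Section 5.8 assigns a multiple linear regression to the association between bone loss and implant A or B. It enters as control variables every factor thought to affect that relationship: sex, age, smoking, cigarettes per day, and then "maxilla or mandible, ISQ [implant stability value] and contact of the mesial and distal implant". The only other comparative test named is this: "The relationship between bone loss and implant position will be analyzed using parametric t-test". No separate model is stated for the ISQ objective.

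**The concern.** Sex, age, smoking history and jaw are settled before allocation, and adjusting for them leaves the meaning of a randomised comparison intact. ISQ is different. It is a property of the allocated implant in the bone, and the choice of implant may change it.

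Conditioning on it causes trouble in two ways. If brand affects ISQ and ISQ in turn affects bone loss, adjustment removes part of the effect that the trial sets out to measure. If brand affects ISQ, and ISQ and bone loss share an unmeasured cause such as bone quality, adjustment creates a brand difference that is not there, or hides one that is. The error can go in either direction.

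At stake is the meaning of the headline result. A reader given only the ISQ-adjusted coefficient could not tell whether a difference, or the lack of one, comes from the brands or from the conditioning.

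**Working it through.** **Inputs from the protocol (5.7).** Target difference 0.2 mm, SD 0.34, two-sided alpha 0.05, power 80%, 5% loss, 48 implants per arm.

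**Reproducing the sample size.** For an unadjusted comparison of two means, n = 2 × (0.34 × (1.960 + 0.842) / 0.2)² = 45.37 per arm. Allowing for loss, 45.37 / 0.95 = 47.75, so 48. The stated figure reproduces, and it rests on a total difference with no adjustment for ISQ.

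**Unadjusted precision.** SE = 0.34 × √(2/48) = 0.0694 mm. Power for 0.2 mm is 81% (noncentral t, implants treated as independent, as in 5.7).

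**Effect of adding ISQ.** Two quantities are needed, and the documents give neither. Both are assumptions:

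- d: difference in mean ISQ between brands, in within-arm SDs;
- g: within-arm slope of bone loss on ISQ, in mm per SD.

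In a linear model the adjusted A/B coefficient is the total effect − d × g. Under 1:1 allocation its variance relative to the unadjusted one is (1 + d²/4) × (1 − (g/0.34)²).

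| d | \|g\| | Shift (mm) | Share of 0.2 mm | Variance ratio |
|---|---|---|---|---|
| 0 | 0.10 | 0 | 0% | 0.913 |
| 0.5 | 0.10 | 0.05 | 25% | 0.971 |
| 0.8 | 0.05 | 0.04 | 20% | 1.135 |
| 0.8 | 0.15 | 0.12 | 60% | 0.934 |

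The SE may fall or rise, so the issue is what is estimated and not how precisely.

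**Middle case, d = 0.5 and |g| = 0.10.** SE = 0.0694 × √0.971 = 0.0684.

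- A true total difference of 0.20 mm is estimated as 0.20 − 0.05 = 0.15 mm or 0.20 + 0.05 = 0.25 mm, depending on the sign of d × g. The chance of significance is about 58% or 95%.
- With a true total difference of 0, the coefficient centres on 0.05 mm in one direction or the other. The chance of significance is about 11%.

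A simulation of 20,000 trials with 48 per arm and a true difference of 0.20 mm gave mean adjusted estimates of 0.149 (g = +0.10), 0.250 (g = −0.10) and 0.200 (d = 0). This confirms the algebra; it says nothing about the actual size of d or g.

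**Shared cause only.** Let an unmeasured factor correlate 0.6 with ISQ and change bone loss by 0.1 mm per SD, with no effect of ISQ itself and no brand effect. Then |g| = 0.6 × 0.1 = 0.06, and d = 0.25 to 0.75 gives a spurious A/B coefficient of 0.015 to 0.045 mm. Simulation agreed. The distortion therefore does not require ISQ to cause bone loss.

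**The case against.** **An ISQ-free comparison may already be planned.** The background often uses position for the level of the implant relative to the crest, and the hypotheses link level to the manufacturer's indications. On that reading the t-test is the unadjusted group comparison, which the sample size formula also suggests. This is a fair reading. But 4.2 has a separate objective on implant location that the t-test could equally serve. Even on the favourable reading, 5.8 would still produce an ISQ-adjusted A/B coefficient without saying which result answers the main objective.

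**The protocol never speaks of a total effect.** True: 4.1 speaks of evaluating bone loss in two brands, and 5.8 of an association. Still, a randomised comparison of brands, sized on a plain difference in means, is most naturally read as the effect of receiving one brand or the other. A later analysis plan could name the primary model, but the protocol has already placed ISQ in the list.

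**The harm is hypothetical.** This stands as a limit on size. Section 5.1 calls the implants similar in design, so a small d is plausible, and at d = 0 there is no bias.

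**The percentages depend on 48 per arm.** Section 5.1 hopes for at least 100 implants per arm. In the middle case with independent implants, power at 0.15 mm would then be about 88%, but the false-positive rate at zero total effect would rise to about 18%. More implants do not remove the shift; they make a spurious difference easier to declare.

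**ISQ has a proper role.** It does, as a secondary objective. That argues for its own model, not for a place in the brand comparison.

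**Conclusion.** The concern holds. The plan conditions its randomised brand comparison on a characteristic of the device measured after allocation. This follows from 4.2, 5.5.1, 5.5.3 and 5.8 and needs no assumption.

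The size of the consequence does rest on assumptions. Over d = 0 to 0.8 SD and |g| = 0.05 to 0.15 mm per SD, the shift runs from 0 to 0.12 mm, that is 0% to 60% of the 0.2 mm target, in an unknown direction. There is no bias if ISQ does not differ by brand, or if it is unrelated to bone loss within arms. The documents do not show which case applies. The point should be corrected because the fix is nearly free; confidence that the distortion is material in this trial is only medium.

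**What to change.** In 5.8, remove ISQ from the control variables of the A/B regression. Adjust only for variables fixed before allocation: age, sex, cigarettes per day, jaw, and neighbouring teeth or implants where these were already present. Add a separate model of bone loss on ISQ for the 4.2 objective, or a labelled exploratory model, and report its result as an association.

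This is a one-line change. It needs no extra data or patients, and the 48 per arm is unaffected because it was calculated without ISQ. The cost is precision if ISQ explains residual variance. When the brands do not differ in ISQ, the SE without it is larger by a factor of 1/√(1 − (g/0.34)²), which is about 1%, 5% or 11% for |g| = 0.05, 0.10 or 0.15.

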### 5.9- Schedule

	2022												2023												
	En	Feb	Mar	Abr	May	Jun	Jul	Agos	Sep	Oct	Nov	Dic	En	Feb	Mar	Abr	May	Jun	Jul	Agos	Sep	Oct	Nov	Dic	
Reclutamiento de participantes																									
2024																									
	En	Feb	Mar	Abr	May	Jun	Jul	Agos	Sep	Oct	Nov	Dic	En	Feb	Mar	Abr	May	Jun	Jul	Agos	Sep	Oct	Nov	Dic	
Recopilación de datos																									
	En	Feb	Mar	Abr	May	Jun	Jul	Agos	Sep	Oct	Nov	Dic	En	Feb	Mar	Abr	May	Jun	Jul	Agos	Sep	Oct	Nov	Dic	
Análisis de los datos																									

### 5.0- Specification of the acceptance of the national and international ethical norms

The researchers agree that each participating subject will be treated and controlled following the protocol authorized by the Ethics and Research Committee for Medicines and Health Products of the Hospital Odontològic of the University of Barcelona (CEIm-HOUB) and the Declaration of Helsinki of ethical principles for medical research in humans by the World Medical Association (64a General Assembly, Fortaleza, Brazil, October 2013).

### 5.1- Economic report

- Cost of rehabilitative prosthetic treatment paid by the patient.
- Administrative costs: in charge of the Master of Dentistry in Medicine surgery and Implant and the doctoral student.
- Material costs: by the Master of Dentistry in Medicine surgery and Implant and the doctoral student.
  - Ortopantografia: 31€.
  - CBCT para un cuadrante: 97€.
  - CBCT para un mono-implant(Dependente en el caso): 81 €.
  - Impressional Alginato Aligsul: 10€.
  - Encerarlo (wax up) GEO CLASSIC gris-OPCA 75GR:20 €.
  - Dental Gypsum (Snow White plaster): 46€.

- Implanto Tipo A: 690€.
- Protesis: 830€.
- Articulado papel (PAPEL BK 01 AZUL 300 HOJAS 0,2mm): 21€.
- Silicona Optosil P Plus (Heraeus Kulzer GmbH, Hanau, Germany): 80€.
- Silicona Zetalabor hard 85 shore A (Zhermack, Badia Polesine, Italy): 120€.
- Guantes de látex (Medicaline, Castellón, España): 180€.

## 5.2- Data collection sheet

### PERSONAL DATA

CODE: IN SESSION:  
NUMBER: SURNAMES:  
DATE: EXAMINER:  
DATE OF BIRTH (AGE): SEX: Man  Woman   
PHONE: E-MAIL:

**TYPE OF PATIENT:** ASA I  ASA II  ASA III  ASA IV  ASA V

**PRIMARY DIAGNOSIS (DATE: mm / yyyy):**

---

---

---

---

